1.1.3. HYPOTHESIS #3

```
PROC FREQ data = <data>;
table VISREAD*COGGRP / fisher;
RUN;
```

1.1.4. HYPOTHESIS #4

```
PROC FREQ data = <data>;
table VISREAD*FIGHTGRP / fisher;
RUN;
```

1.2.SAMPLE CODE FOR EXPLORATORY ENDPOINT

```
ods output PearsonCorr=corr;  
PROC CORR data = <data> pearsons;  
var <variable list>;  
RUN;
```

1.3.SAMPLE CODE FOR TEAE TABLES BY DESCENDING FREQUENCY

```
ods output crosstabfreqs=xtab;  
PROC FREQ data = <data> order=freq;  
table <SOC variable>*<Preferred Term variable>;  
RUN;
```

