Protocol Number: ^{18}F -AV-1451-A11

^{18}F -AV-1451 PET Imaging in Professional Fighters

Date and Version:

13 July 2015, Amendment 1

[figure not shown]
Name of Compound:

^{18}F -AV-1451 ([F-18]T807)

Sponsor:

Avid Radiopharmaceuticals
Philadelphia, Pennsylvania USA

Approvals/Signatures and Date:

CONFIDENTIAL

This material is the property of Avid Radiopharmaceuticals (Avid). The information is confidential and is to be used only in connection with matters authorized by Avid and no part of it is to be disclosed to others without prior written permission from Avid.

Sponsor: Avid Radiopharmaceuticals	Name of Compound: ¹⁸ F-AV-1451([F-18]T807)	Active Ingredient(s): 7-(6-[F-18]fluoropyridin-3-yl)-5H-pyrido[4,3-b]indole
Title of Study: ¹⁸ F-AV-1451-A11 “ ¹⁸ F-AV-1451 PET Imaging in Professional Fighters”		
Planned number of subjects (Enrolled): Approximately 30 This study will be divided into the following groups: 
 1. Approximately 15 active professional fighters (boxers and mixed martial artists) who have had at minimum 10 professional fights. 
 a. Approximately 10 with cognitive impairment b. Approximately 5 without cognitive or behavioral complaints 2. Approximately 15 retired professional fighters (boxers and mixed martial artists). 
 a. Approximately 10 with cognitive impairment b. Approximately 5 without cognitive or behavioral complaints Subjects will be recruited from the pool of participants in the Professional Fighters Brain Health Study (PFBHS).		
Name of compound: ¹⁸ F-AV-1451([F-18]T807) Dose: 370 MBq (10 mCi) Route of Administration: Intravenous (IV) bolus		
Study Phase: I		
Study Centers: 1-3 centers in the United States		
Trial Objectives: The primary objectives of this study are: 
 • To explore the use of ¹⁸F-AV-1451 as a biomarker for brain injury related to repetitive head trauma; and • To examine the relationship between clinical presentation and tau deposition as measured by ¹⁸F-AV-1451 uptake in active and retired professional fighters. A secondary objective of this study is: 
 • To expand the ¹⁸F-AV-1451 safety database. 		
Eligibility: Only subjects duly consented and enrolled in the PFBHS protocol (conducted by the Cleveland Clinic with [name] as Principal Investigator) will be considered for participation in this study (see Section 5.3, Selection of Subjects).		

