10.1.4. Exploratory Analysis

A correlation analysis will be performed to investigate the relationship between flortaucipir SUVR and:

- MMSE
- Beck Depression Inventory II
- Digit span forward/backward
- MRI brain volumes (normalized to intracranial volume)
 - Whole brain volume
 - Gray volume
 - Hippocampal volume
 - Ventricle volume

Contingent on a trending significance in the primary analysis ($p \leq 0.1500$ for contrasts), more correlation analysis will be performed to investigate the relationship between tau deposition as measured by flortaucipir SUVR and:

- Years of fighting
- Age when fighting began
- Number of bouts
- Number of losses
- Number of wins
- Number of draws
- Number of knockouts

A multivariate model may also be derived assuming strong relationships found in the primary and correlation analyses.

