10.1.4.1. Subgroup Analysis

All correlation analysis conducted will be performed for each cognitive group separately, and results will be provided in a table.

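### The only correlation method the SAP names is Pearson, in groups of about 20 and 10, with no planned check on whether one fighter drives a result

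*SAP*

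**What the plan says.** SAP 10.1.4 (Exploratory Analysis) opens with "A correlation analysis will be performed to investigate the relationship between flortaucipir SUVR and", followed by MMSE, Beck Depression Inventory II, digit span forward and backward, and four MRI volumes. If a primary contrast reaches p of 0.15 or less, seven fight-history variables are added, among them bouts, losses and knockouts. The section names no correlation method.

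The method appears only in SAP Appendix II, 1.2 (Sample Code for Exploratory Endpoint). The template requests "PROC CORR data = <data> pearsons" and keeps one output table, "ods output PearsonCorr=corr".

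SAP 10.1.4.1 adds: "All correlation analysis conducted will be performed for each cognitive group separately, and results will be provided in a table". For both active and retired fighters, the protocol synopsis plans "Approximately 10 with cognitive impairment" and "Approximately 5 without cognitive or behavioral complaints".

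On later use, SAP 10.1.4 says: "A multivariate model may also be derived assuming strong relationships found in the primary and correlation analyses". It does not define strong.

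Two provisions come close to a check, but neither covers the correlations. Protocol 8.1 allows Kruskal-Wallis and Wilcoxon tests when assumptions fail, for group comparisons only. SAP 10.1.3 plans box plots of SUVr by enrolment group, which do not pair SUVr with a score.

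**The concern.** Pearson r is built from products of deviations, so in a group of 10 or 20 one subject far out on both variables can supply most of the coefficient. The planned variables make awkward shapes plausible: MMSE is bounded at 30, the depression score may be skewed, and the fight variables, if triggered, are mostly counts.

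The trial will have one data set. A method can hold its error rate over repeated sampling and still give an r in that data set that reflects one fighter. A table of Pearson coefficients cannot show the difference. At stake is how the exploratory findings are described: a relationship reported for a cognitive group, and possibly used in choosing variables for a multivariate model, could rest on one person without the report saying so.

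**Working it through.** The documents give no power, detectable correlation or distribution for these analyses, so there is no planned figure to reproduce.

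**Inputs.** Impaired 10 + 10 = 20; unimpaired 5 + 5 = 10; total 30 (protocol synopsis). Alpha 0.05 without multiplicity adjustment (SAP 10.1.3.1). Two-sided testing is assumed, since sidedness is not stated for correlations. Two SUVr measures are analysed separately (SAP 10.1.1).

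**Scope.** 2 SUVr measures × 8 variables × 2 groups = 32 correlations (digit span forward and backward counted separately). With the seven fight variables: 2 × 15 × 2 = 60.

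**Critical value.** |r| = t/√(n − 2 + t²), with t the two-sided 5% point on n − 2 df. This gives 0.632 (n = 10), 0.444 (n = 20) and 0.361 (n = 30, if a pooled analysis is also run).

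**What one fighter can do.** Let the other n − 1 fighters have r exactly 0 and unit SD, and place one fighter k SD from their mean on both variables. Then r = S/(n − 2 + S), with S = k²(n − 1)/n.
- n = 10, k = 4: S = 16 × 9/10 = 14.4; r = 14.4/22.4 = 0.643; p = 0.045.
- n = 20, k = 4: S = 16 × 19/20 = 15.2; r = 15.2/33.2 = 0.458; p = 0.042.
- k = 3: r = 0.503, p = 0.14 (n = 10); r = 0.322, p = 0.17 (n = 20).

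The distance at which one fighter alone gives p = 0.05 is 3.91 SD (n = 10), 3.89 SD (n = 20) or 4.05 SD (n = 30).

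**Simulation.** 20,000 data sets per row: independent normal variables, with one fighter fixed at k SD on both. Spearman uses the same critical value, which is approximate. Entries are the percentage nominally significant.

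| n | k | Pearson | Spearman | Pearson without that fighter |
|---|---|---|---|---|
| 10 | none | 5.0 | 5.6 | 4.9 |
| 10 | 2 | 11.4 | 7.8 | 5.0 |
| 10 | 3 | 30.2 | 8.8 | 5.0 |
| 10 | 4 | 59.1 | 8.4 | 4.8 |
| 20 | none | 5.3 | 5.3 | 5.3 |
| 20 | 2 | 9.5 | 6.6 | 4.9 |
| 20 | 3 | 26.2 | 6.9 | 5.1 |
| 20 | 4 | 58.0 | 7.6 | 5.1 |
| 30 | 4 | 52.2 | 6.3 | 5.0 |

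Spearman barely changes with k because a fighter already ranked highest on both variables adds no more by moving further out.

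**Would a second coefficient reveal it?** A repeat run with the fighter at 4 SD in opposite directions (high uptake, low score) gave median Pearson r of −0.67 (n = 10) and −0.47 (n = 20), against Spearman −0.27 and −0.14. Where Pearson was significant, Spearman was not in 85% and 88% of data sets.

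**Skewed data with no imposed outlier.** With independent, oppositely skewed variables (lognormal, an assumption), Pearson's overall error stays at 5-6%. Its false positives in the direction of higher uptake with worse score run at about 5% against a nominal 2.5%; Spearman gives 2.6-2.8%.

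**The case against.** The strongest reply is that the 58-59% is stipulated. A reader might take it as the false-positive rate of the planned analysis. It is not: every simulated data set contains a fighter placed at 4 SD on both variables. With independent normal variables, the chance that any fighter exceeds 3 SD in either direction on both is about 10 × 0.0027² = 0.007% at n = 10 and 0.015% at n = 20. An outlier on one variable alone leaves Pearson at 5.1% and 4.7%. A fighter extreme on both uptake and score may also be the real signal. All of this stands. It limits the claim to a missing check and rules out any claim of inflated error.

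It also stands that the template is labelled sample code and the SAP body leaves the method open; that the by-group rule sits under a subgroup heading, so a pooled analysis of about 30 may also be run; and that extremes are not hidden, since minima, maxima, box plots and subject listings are planned. However, no other correlation method is named anywhere, a pooled analysis is still sensitive (52% at 4 SD), and no planned display pairs SUVr with a score or ties any action to an extreme value.

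A last argument is that Spearman may lose power. In a skewed monotone example, Pearson and Spearman had 40% and 35% power at n = 10, and 64% and 69% at n = 20. That matters if one replaces the other. It is no argument against reporting both.

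**Conclusion.** The concern holds as a minor, inexpensive improvement. The SAP's only named correlation method is sensitive to a single subject at these group sizes, and nothing planned would show when a result depends on one. The size rests on an assumed outlier distance: a modest effect at 2 SD (about 10-11% nominally significant), substantial at 3 SD (26-30%) and large at 4 SD (58-59%), against about 7-9% for Spearman.

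Two stronger readings are not supported. A reader might infer that these correlations are the main evidence for the second primary objective, clinical presentation against tau. But Hypotheses 1 and 3, tested under the SAP's Primary Analysis, also compare uptake by cognitive status, and SAP 10.1.2 labels all testing exploratory. A reader might also infer that a one-fighter correlation would pass automatically into a model. The multivariate model is optional and calls for strong relationships in the primary as well as the correlation analyses, and no p-value rule defines strong. The fight counts enter only if the 0.15 trigger is met.

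**What to change.** In SAP 10.1.4, name the method: Pearson and Spearman for every pair, with a scatter plot, in each group in which the correlation is run. In Appendix II 1.2, request PEARSON and SPEARMAN and keep both ODS tables.

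For any correlation described as strong or considered for the multivariate model, report the leave-one-out range: the smallest and largest Pearson r obtained when each fighter is omitted in turn. State in the report when the relationship depends on one fighter. That fighter stays in the analysis.

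A rule that Spearman must agree in direction and rough size would be a poor substitute. In the 4 SD scenario, among Pearson-significant data sets, the signs agree in 95-96%, and the coefficients lie within 0.3 of each other in 42-50%. Requiring both to be significant would cut power at a true correlation of 0.6 from 49% to 37% (n = 10) and from 84% to 75% (n = 20), so Spearman should not become a second hurdle.

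The cost is a few sentences and small code edits, plus a second coefficient and a plot for each of 32 to 60 pairs. No new data are needed and Pearson is not replaced.
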